10.1.2 Procedures for reporting and recording adverse events

The subject or subject's parent(s)/caregiver(s)/legal representative(s) will be given the opportunity to report AEs spontaneously. A general prompt will also be given at each study visit to detect AEs. For example:

“Did you notice anything unusual about your health (since your last visit)?”

In addition, the investigator should review any self-assessment procedures (eg, diary cards) employed in the study.

10.1.3 Description of adverse events

When recording an AE, the investigator should use the overall diagnosis or syndrome using standard medical terminology, rather than recording individual symptoms or signs. The eCRF and source documents should be consistent. Any discrepancies between the subject's own words

on his/her own records (eg, diary card) and the corresponding medical terminology should be clarified in the source documentation.

Details for completion of the Adverse Event eCRF (including judgment of relationship to study drug) are described in the eCRF Completion Guidelines.

10.1.4 Follow up of adverse events

An AE should be followed until it has resolved, has a stable sequelae, the investigator determines that it is no longer clinically significant, or the subject is lost to follow up.

If an AE is ongoing at the end of the study for a subject, follow up should be provided until resolution/stable level of sequelae is achieved, or until the investigator no longer deems that it is clinically significant, or until the subject is lost to follow up. If no follow up is provided, the investigator must provide a justification. The follow up will usually be continued for 30 days after the subject has discontinued his/her IMP.

10.1.5 Rule for repetition of an adverse event

An increase in the intensity of an AE should lead to the repetition of the AE being reported with:

- The outcome date of the first AE that is not related to the natural course of the disease being the same as the start date of the repeated AE, and the outcome of “worsening”
- The AE verbatim term being the same for the first and repeated AE, so that the repeated AE can be easily identified as the worsening of the first one

10.1.6 Pregnancy

Should a subject become pregnant after the first intake of any IMP, UCB’s Drug Safety department should be informed immediately. The subject should be withdrawn from the study as soon as pregnancy is known, and the following should be completed:

- The subject should return for an Early Termination Visit.
- The subject should immediately stop the intake of the IMP or be down-titrated as instructed at the Early Termination Visit.
- A Safety Follow-Up Visit should be scheduled 2 weeks (± 2 days) after the subject has discontinued IMP.

The investigator must inform the subject of information currently known about potential risks and about available treatment alternatives.

In cases where the partner of a male subject enrolled in a clinical study becomes pregnant, UCB will ask the investigator or designee to contact the subject and his partner to request consent via the Partner Pregnancy Consent form. If the partner agrees to provide additional information, the Pregnancy Report and Outcome form will be forwarded to the subject’s partner for completion.

The pregnancy will be documented on the Pregnancy Report and Outcome form provided to the investigator. The progression of the pregnancy and the eventual birth (if applicable) must be followed-up using the Pregnancy Report and Outcome form in which the investigator has to report on the health of the mother and of the child. The health of the child must be followed for 30 days after birth for any significant medical issues.

In certain circumstances, UCB may request that follow up is continued for a period longer than 30 days.

A pregnancy becomes an SAE in the following circumstances: miscarriage, abortion, or anomaly/birth defect of the child. Those SAEs must be additionally reported using the Investigator SAE Report form.

10.1.7 Overdose of IMP

Excessive dosing (beyond that prescribed in the protocol and including overdose) should be recorded in the Drug Accountability or Study Drug Dosing module of the eCRF. Any SAE or nonserious AE associated with excessive dosing must be followed as any other SAE or nonserious AE. These events are only considered AEs or SAEs if there are associated clinical signs and symptoms or if the act of taking the excess medicine itself is an AE or SAE (eg, suicide attempt).

10.1.8 Safety signal detection

Selected data from this study will be reviewed periodically to detect as early as possible any safety concern(s) related to the IMP so that investigators, clinical study subjects, regulatory authorities, and IRBs/IECs will be informed appropriately and as early as possible.

The Study Physician or medically qualified designee/equivalent will conduct an ongoing review of SAEs and perform ongoing SAE reconciliations in collaboration with the Drug Safety representative.

As appropriate for the stage of development and accumulated experience with the IMP, medically qualified personnel at UCB may identify additional safety measures (eg, AEs, vital signs, laboratory or ECG results) for which data will be periodically reviewed during the course of the study.

10.1.9 Occurrence of COVID-19

Occurrence of COVID-19 in subjects should be reported as either “suspected COVID-19” or “confirmed COVID-19” along with all available relevant data including diagnostic and laboratory data. For subjects where COVID-19 is still suspected despite a negative viral test, please report as “suspected COVID-19” and provide relevant data to support the diagnosis as well as the test results.

10.2 Serious adverse events

10.2.1 Definition of serious adverse event

Once it is determined that a subject experienced an AE, the seriousness of the AE must be determined. An SAE must meet 1 or more of the following criteria:

- Death
- Life-threatening
(Life-threatening does not include a reaction that might have caused death had it occurred in a more severe form.)
- Significant or persistent disability/incapacity

- Congenital anomaly/birth defect (including that occurring in a fetus)
- Important medical event that, based upon appropriate medical judgment, may jeopardize the patient or subject and may require medical or surgical intervention to prevent 1 of the other outcomes listed in the definition of serious

(Important medical events may include but are not limited to, potential Hy's Law [see Section 10.3], allergic bronchospasm requiring intensive treatment in an emergency room or at home, blood dyscrasias that do not result in inpatient hospitalization, or the development of drug dependency or drug abuse.)

- Initial inpatient hospitalization or prolongation of hospitalization

(A patient admitted to a hospital, even if he/she is released on the same day, meets the criteria for the initial inpatient hospitalization. An emergency room visit that results in admission to the hospital would also qualify for the initial inpatient hospitalization criteria. However, emergency room visits that do not result in admission to the hospital would not qualify for this criteria and, instead, should be evaluated for 1 of the other criteria in the definition of serious [eg, life-threatening adverse experience, important medical event].

Hospitalizations for reasons not associated with the occurrence of an AE [eg, preplanned surgery or elective surgery for a pre-existing condition that has not worsened or manifested in an unusual or uncharacteristic manner] do not qualify for reporting. For example, if a subject has a condition recorded on his/her medical history and later has a preplanned surgery for this condition, it is not appropriate to record the surgery or hospitalization as an SAE, since there is no AE upon which to assess the serious criteria. Please note that, if the pre-existing condition has worsened or manifested in an unusual or uncharacteristic manner, this would then qualify as an AE and, if necessary, the seriousness of the event would need to be determined.)

10.2.2 Procedures for reporting serious adverse events

If an SAE is reported, UCB must be informed within 24 hours of receipt of this information by the site (see contact information for SAE reporting listed in the Serious Adverse Event Reporting section at the front of the protocol). The investigator must forward to UCB (or its representative) a duly completed "Investigator SAE Report Form for Development Drug" (SAE report form) provided by UCB, even if the data are incomplete, or if it is obvious that more data will be needed in order to draw any conclusions. Information recorded on this form will be entered into the global safety database.

An Investigator SAE report form will be provided to the investigator. The Investigator SAE report form must be completed in English.

It is important for the investigator, when completing the SAE report form, to include the assessment as to a causal relationship between the SAE and the IMP administration. This insight from the investigator is very important for UCB to consider in assessing the safety of the IMP and in determining whether the SAE requires reporting to the regulatory authorities in an expedited manner.

Additional information (eg, autopsy or laboratory reports) received by the investigator must be provided within 24 hours. All documents in the local language must be accompanied by a

translation in English, or the relevant information included in the same document must be summarized in the Investigator SAE report form.

The investigator is specifically requested to collect and report to UCB (or its representative) any SAEs (even if the investigator is certain that they are in no way associated with the IMP), up to 30 days from the end of the study for each subject, and to also inform participating subjects of the need to inform the investigator of any SAE within this period. Serious AEs that the investigator thinks may be associated with the IMP must be reported to UCB regardless of the time between the event and the end of the study.

Upon receipt of the SAE report form, UCB will perform an assessment of expectedness of the reported SAE. The assessment of the expectedness of the SAE is based on the Investigator's Brochure.

10.2.3 Follow up of serious adverse events

An SAE should be followed until it has resolved, has a stable sequelae, the investigator determines that it is no longer clinically significant, or the subject is lost to follow up.

Information on SAEs obtained after clinical database lock will be captured through the Drug Safety database without limitation of time. This follow up requirement applies to AEs, SAEs, and AEs of special interest; further details regarding follow up of PDILI events are provided in Section 10.6.1.

10.3 Adverse events of special interest

An AE of special interest is any AE that a regulatory authority has mandated be reported on an expedited basis, regardless of the seriousness, expectedness, or relatedness of the AE to the administration of a UCB product/compound.

The following are AEs of special interest:

- The following arrhythmias: atrial fibrillation/flutter, ventricular tachycardia or fibrillation, AV block (second-degree Type I and II and third-degree), and marked bradycardia (<45beats/min)
- Syncope or loss of consciousness (other than seizure-related)
- Serious suspected multiorgan hypersensitivity reactions

Serious suspected multiorgan hypersensitivity cases may be identified and reported to the sponsor by the investigator using the following algorithm as agreed with the US Food and Drug Administration:

- An AE or laboratory value (as defined in the following text) suggestive of internal organ involvement (including but not limited to hepatitis, nephritis, pneumonitis, carditis, colitis, encephalitis, pancreatitis, myositis, arthritis, or hematologic system involvement) combined with at least 1 of the following: fever, rash, lymphadenopathy, or eosinophilia.

Treatment-emergent abnormal laboratory value criteria suggestive of internal organ involvement or eosinophilia:

- Eosinophils % $\geq 10\%$
- Eosinophils absolute $\geq 0.5G/L$

- Neutrophils absolute <1.5G/L
 - Platelets \leq 100G/L
 - ALT \geq 2 \times ULN
 - AST \geq 2 \times ULN
- Potential Hy's Law, defined as \geq 3 \times ULN ALT or AST with coexisting \geq 2 \times ULN total bilirubin in the absence of \geq 2 \times ULN ALP, with no alternative explanation for the biochemical abnormality, must ALWAYS be reported to UCB as an AE of special interest (ie, without waiting for any additional etiologic investigations to have been concluded). Follow-up information should then be reported if an alternative etiology is identified during investigation and monitoring of the subject.

10.4 Immediate reporting of adverse events

The following AEs must be reported immediately:

- SAE: AE that the investigator classifies as serious by the above definitions regardless of causality
- Suspected transmission of an infectious agent via a medicinal product
- AE of special interest (see Section 10.3)

10.5 Anticipated serious adverse events

The following list of Anticipated SAEs has been identified, as these events are anticipated to occur in the population studied in this protocol at some frequency that is independent of drug exposure. This original list will remain in effect for the duration of the protocol.

This list does not change the investigator's obligation to report all SAEs (including Anticipated SAEs) as detailed in Section 10.2.2.

Table 10–1: Anticipated SAEs for the pediatric epilepsy population

MedDRA SOC	MedDRA PT
Congenital, familial and genetic disorders	Teratogenicity
General disorders and administration site conditions	Sudden unexplained death in epilepsy
Nervous system disorders	Convulsion
	Incontinence
	Status epilepticus
Pregnancy, puerperium and perinatal disorders	Abortion spontaneous
Psychiatric disorders	Psychotic behaviour
	Abnormal behaviour
	Anxiety
	Sleep disorder
Reproductive system and breast disorders	Menstrual disorder

MedDRA=Medical Dictionary for Regulatory Activities; PT=preferred term; SOC=system organ class; SAE=serious adverse event

10.6 Laboratory measurements

Blood and urine specimens for routine assay of hematology, clinical chemistry, endocrinology, and urinalysis testing will be collected according to the tabular schedules of study procedures (Section 5.2). Urine assessments will be performed for subjects aged ≥ 5 years. For subjects aged ≥ 5 years, urine assessments will be based on the subject's ability to void and staff's ability to collect urine (in an appropriate container). A central laboratory will perform the routine analysis of blood and urine specimens. Pregnancy testing will also be performed (see Section 10.7). The procedures for handling and shipping these specimens will be provided to the sites. In exceptional circumstances, local laboratory analysis may be performed. The medical monitor should be contacted beforehand to discuss these circumstances.

The following laboratory parameters will be measured:

Table 10–2: Laboratory measurements

Hematology	Chemistry	Endocrinology	Urinalysis ^a
Hematocrit	Calcium	FSH	pH
Hemoglobin	Phosphorus	LH	Ketones
Platelet count	Serum electrolytes (sodium, potassium, chloride, bicarbonate)	Testosterone	Glucose
RBC count	Creatinine	TSH	Albumin
WBC count	BUN	T ₃ (total and serum free)	Specific gravity
Differential count	AST	T ₄ (total and serum free)	Microscopic exam for blood cells or casts/hpf
	ALT		
	Total bilirubin		
	Alkaline phosphatase		
	GGT		
	Glucose		
	Albumin		
	Total serum protein		
	Uric acid		
	Total cholesterol		
	Triglycerides		

ALT=alanine aminotransferase; AST=aspartate aminotransferase; BUN=blood urea nitrogen; FSH=follicle stimulating hormone; GGT=gamma-glutamyltransferase; hpf=high power field; LH=luteinizing hormone; RBC=red blood cells; T₃=triiodothyronine; T₄=thyroxine; TSH=thyroid stimulating hormone; WBC=white blood cell

^a Urinalysis will be performed for subjects ≥5 years of age only.

10.6.1 Liver function tests and evaluation of PDILI

The PDILI IMP discontinuation criteria for this study are provided in Section 10.6.1.2, with the accompanying required follow-up investigation and monitoring detailed below. All PDILI events must be reported as an AE and reported to the study site and sponsor within 24 hours of learning of their occurrence. Any PDILI event that meets the criterion for potential Hy’s Law must be reported as an AE of special interest (see Section 10.3), and, if applicable, also reported as an SAE (see Section 10.2).

Evaluation of PDILI consists of the diagnostic testing and continued monitoring included in Table 10–3 (specific tests dependent on laboratory results and corresponding symptoms) and consultation with a local hepatologist (if applicable; discussed in Section 10.6.1.1). The local

hepatologist is the expert usually consulted by the treating physician for assessment and management of potential hepatic disease. This would usually be a hepatologist, but may be a gastroenterologist. Additional investigation and monitoring may be required and adapted based on the diagnosis after the cause of the liver injury/abnormality is confirmed (details in Section 10.6.1.4).

The results of all monitoring, including laboratory testing and other testing, should be made available to the study site and sponsor.

All initial tests resulting in abnormal hepatic laboratory values need to be repeated, but appropriate medical action must not be delayed waiting for the repeat result.

If tests are done locally for more rapid results, a concurrent sample should also be sent to the central laboratory whenever possible. Medical care decisions are to be made initially using the most rapidly available results and a conservative approach must be taken if the results from the 2 laboratory tests are significantly different. Data from the local and central laboratory are to be recorded on the applicable eCRF pages.

When IMP is discontinued, all concomitant medications and herbal supplements that are not medically necessary should also be discontinued. In these cases, the investigator should also consider dose reduction for medically necessary concomitant medication and consider changing any medically required concomitant medication known to be hepatotoxic to a suitable alternative.

When IMP is stopped due to PDILI (as described in Section 6.3.1), IMP must be permanently discontinued unless a subsequent alternative diagnosis fully explains the hepatic findings. Rechallenge with a substance potentially causing drug-induced liver injury is dangerous, may be fatal, and must not occur.

Table 10–3 below summarizes the approach to investigate PDILI.

Table 10–3: Required investigations and follow up for PDILI

Laboratory value			Immediate		Follow up	
ALT or AST	Total bilirubin	Symptoms ^a of hepatitis or hypersensitivity	Consultation requirements	Actions	Testing	Evaluation
≥3xULN	≥2xULN ^b	NA	Hepatology consult. ^c	Immediate, permanent IMP discontinuation.	Essential: Must have repeat liver chemistry values and additional testing completed ASAP (see Section 10.6.1.3); recommended to occur at the site with HCP.	Monitoring of liver chemistry values at least twice per week until values normalize, stabilize, or return to within Baseline values. ^d
≥5xULN	NA	Medical Monitor must be notified within 24 hours (eg, by laboratory alert) and subject discussed with Medical Monitor ASAP.				
≥3xULN	NA	Yes		Immediate, permanent IMP discontinuation.		
≥3xULN (and ≥2x Baseline) and <5xULN	<2xULN	No	Discussion with Medical Monitor required if the criterion that allows for IMP continuation is met.	Further investigation – immediate IMP discontinuation not required (see Section 10.6.1.2).	Not required unless otherwise medically indicated (at discretion of investigator).	
≥5xULN (and ≥2x Baseline)	<2xULN	No	Discussion with Medical Monitor required.	Immediate, permanent IMP discontinuation.	Essential: Every attempt must be made to have repeat liver chemistry values and additional testing completed within 48 hours at the site with HCP (see Section 10.6.1.3).	Monitoring of liver chemistry values at least twice per week until values normalize, stabilize, or return to within Baseline values. ^d

Table 10–3: Required investigations and follow up for PDILI

Laboratory value			Immediate		Follow up	
ALT or AST	Total bilirubin	Symptoms ^a of hepatitis or hypersensitivity	Consultation requirements	Actions	Testing	Evaluation

ALP=alkaline phosphatase; ALT=alanine aminotransferase; ASAP=as soon as possible; AST=aspartate aminotransferase; HCP=healthcare practitioner; IMP=investigational medicinal product; NA=not applicable; PDILI=potential drug-induced liver injury; ULN=upper limit of normal

^a Hepatitis symptoms include fatigue, nausea, vomiting, and right upper quadrant pain or tenderness; hypersensitivity symptoms include eosinophilia (>5%), rash, and fever (without clear alternative cause).

^b If the subject also has $\geq 2 \times$ ULN ALP, the possibility of an indication of biliary obstruction should be discussed with the Medical Monitor.

^c Details provided in [Section 10.6.1.1](#). The local hepatologist is the expert usually consulted by the treating physician for assessment and management of potential hepatic disease. This would usually be a hepatologist, but may be a gastroenterologist.

^d Unless an alternative monitoring schedule is agreed by the investigator and UCB responsible physician. Determination of stabilization is at the discretion of the investigator in consultation with the hepatologist (as applicable) and UCB responsible physician, as needed

10.6.1.1 Consultation with Medical Monitor and local hepatologist

Potential drug-induced liver injury events require notification of the Medical Monitor within 24 hours (eg, by laboratory alert), and the subject must be discussed with the Medical Monitor as soon as possible. If required, the subject must also be discussed with the local hepatologist. The local hepatologist is the expert usually consulted by the treating physician for assessment and management of potential hepatic disease. This would usually be a hepatologist, but may be a gastroenterologist. If determined necessary, this discussion should be followed by a full hepatology assessment (see Section 10.6.1.3) and SAE report (if applicable).

10.6.1.2 Immediate action: determination of IMP discontinuation

All PDILI events require immediate action, testing, and monitoring.

The immediate action is dependent on the laboratory values and symptoms of hepatitis or hypersensitivity and ranges from continuation of IMP (followed by immediate investigation) to immediate and permanent discontinuation (see Section 6.3.1 and Table 10-3 for details).

When IMP is discontinued, all concomitant medications and herbal supplements that are not medically necessary should also be discontinued. The investigator should also consider dose reduction for medically necessary concomitant medication and consider changing any medically required concomitant medication known to be hepatotoxic to a suitable alternative.

10.6.1.3 Testing: identification/exclusion of alternative etiology

The measurements and additional information required for the assessment of PDILI events when there is a reasonable possibility that they may have been caused by the IMP are detailed in Table 10-4 (laboratory measurements) and Table 10-5 (additional information). Results of the laboratory measurements and information collected are to be submitted to the sponsor on the corresponding eCRF. If the medical history of the subject indicates a requirement for other assessments not included below, these additional assessments should be completed and submitted, as applicable.

All blood samples should be stored, if possible. If tests are done locally for more rapid results, a concurrent sample must also be sent to the central laboratory.

The following measurements are to be assessed:

Table 10-4: PDILI laboratory measurements

Virology-related	Hepatitis A IgM antibody
	HBsAg
	Hepatitis E IgM antibody
	HBcAb-IgM
	Hepatitis C RNA
	Cytomegalovirus IgM antibody

Table 10–4: PDILI laboratory measurements

	Epstein-Barr viral capsid antigen IgM antibody (if unavailable, obtain heterophile antibody or monospot testing)
Immunology	Anti-nuclear antibody (qualitative and quantitative)
	Anti-smooth muscle antibody (qualitative and quantitative)
	Type 1 anti-liver kidney microsomal antibodies (qualitative and quantitative)
Hematology	Hematocrit
	Hemoglobin
	Platelet count
	RBC count
	WBC count
	Differential count
Urinalysis	Toxicology screen
Chemistry	Amylase
	Bilirubin (If total bilirubin $\geq 1.5 \times \text{ULN}$, obtain fractionated bilirubin to obtain % direct bilirubin)
	Serum CPK and LDH to evaluate possible muscle injury causing transaminase elevation
	AST
	ALT
	ALP
	GGT
	Albumin
Additional	Prothrombin time/INR ^a
	Serum pregnancy test in women of childbearing potential
	PK sample

ALP=alkaline phosphatase; ALT=alanine aminotransferase; AST=aspartate aminotransferase; CPK=creatine phosphokinase; GGT=gamma-glutamyltransferase; HBcAb-IgM=hepatitis B core antibody-IgM; HBsAg=hepatitis B surface antigen; IgM=immunoglobulin M; INR=international normalized ratio; LDH=lactate dehydrogenase; PDILI=potential drug-induced liver injury; PK=pharmacokinetic; RBC=red blood cell; RNA=ribonucleic acid; ULN=upper limit of normal; WBC=white blood cell

^a Measured only for subjects with ALT $> 8 \times \text{ULN}$, elevations in total bilirubin, and symptoms of hepatitis or hypersensitivity. Hepatitis symptoms include fatigue, nausea, vomiting, and right upper quadrant pain or tenderness; hypersensitivity symptoms include eosinophilia ($> 5\%$), rash, and fever (without clear alternative cause).

The following additional information is to be collected:

Table 10–5: PDILI information to be collected

New or updated information
Concomitant prescription and over-the-counter medications (eg, acetaminophen, herbal remedies, vitamins); dosages and dates should be included.
Pertinent medical history, including the following: 
 • History of liver disease (eg, autoimmune hepatitis, nonalcoholic steatohepatitis or other “fatty liver disease”) • Adverse reactions to drugs • Allergies • Relevant family history or inheritable disorders (eg, Gilbert’s syndrome, alpha-1 antitrypsin deficiency) • Recent travel • Progression of malignancy involving the liver (Note: Metastatic disease to the liver, by itself, should not be used as an explanation for significant AST and/or ALT elevations.)
The appearance or worsening of clinical symptoms of hepatitis or hypersensitivity (eg, fatigue, nausea, vomiting, right upper quadrant pain or tenderness, decreased appetite, abdominal pain, jaundice, fever, or rash)
Recent clinically significant hypotension or hypoxemia with compromised cardiopulmonary function
Alcohol and illicit drug use
Results of liver imaging or liver biopsy, if done
Results of any specialist or hepatology consult, if done
Any postmortem/pathology reports

ALT=alanine aminotransferase; AST=aspartate aminotransferase; PDILI=potential drug-induced liver injury

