6.3.1 Potential drug-induced liver injury IMP discontinuation criteria

Subjects with potential drug-induced liver injury (PDILI) must be assessed to determine if investigational medicinal product (IMP) must be immediately and permanently discontinued. In addition, all concomitant medications and herbal supplements that are not medically necessary should also be discontinued.

The PDILI criteria below require immediate and permanent discontinuation of IMP:

- Subjects with either of the following:
 - ALT or AST $\geq 5 \times \text{ULN}$
 - ALT or AST $\geq 3 \times \text{ULN}$ and coexisting total bilirubin $\geq 2 \times \text{ULN}$

The PDILI criterion below requires immediate discontinuation of IMP:

- Subjects with ALT or AST $\geq 3 \times \text{ULN}$ who exhibit temporally associated symptoms of hepatitis or hypersensitivity. Hepatitis symptoms include fatigue, nausea, vomiting, right upper quadrant pain or tenderness. Hypersensitivity symptoms include fever (without clear alternative cause), rash, or eosinophilia (ie, $>5\%$).

The PDILI criterion below allows for subjects to continue on IMP at the discretion of the investigator.

- Subjects with ALT or AST $\geq 3 \times \text{ULN}$ (and $\geq 2 \times$ Baseline), and $< 5 \times \text{ULN}$, total bilirubin $< 2 \times \text{ULN}$, and no eosinophilia (ie, $\leq 5\%$), with no fever, rash, or symptoms of hepatitis (eg, fatigue, nausea, vomiting, right upper quadrant pain or tenderness)

Evaluation of PDILI must be initiated as described in Section 10.6.1. If subjects are unable to comply with the applicable monitoring schedule, IMP must be discontinued immediately.

Investigators should attempt to obtain information on subjects in the case of IMP discontinuation to complete the final evaluation. Subjects with PDILI should not be withdrawn from the study until investigation and monitoring are complete. All results of these evaluations and observations, as well as the reason(s) for IMP discontinuation and subject withdrawal (if applicable), must be recorded in the source documents. The eCRF must document the primary reason for IMP discontinuation.

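### The PT/INR trigger in Table 10-4 is narrower than the protocol's own potential Hy's Law definition, so a child can meet that definition with no protocol-required INR

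*Protocol*

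**What the plan says.** Table 10-4 (Protocol 10.6.1.3) sets out the laboratory work-up for a potential drug-induced liver injury (PDILI) event. Its last block includes "Prothrombin time/INR ^a", and footnote a reads "Measured only for subjects with ALT $> 8 \times \text{ULN}$, elevations in total bilirubin, and symptoms of hepatitis or hypersensitivity". The footnote then lists what counts as a symptom. PT/INR is the only clotting test in the table.

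Three other places define the cases the protocol treats as most serious:

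- Section 10.3 defines potential Hy's Law as ALT or AST ≥3×ULN together with total bilirubin ≥2×ULN, no ALP ≥2×ULN and no alternative explanation. Such a case "must ALWAYS be reported to UCB as an AE of special interest", without waiting for the etiologic work-up to finish.
- Section 6.3.1, under the words "The PDILI criteria below require immediate and permanent discontinuation of IMP", lists ALT or AST ≥3×ULN with total bilirubin ≥2×ULN (and, separately, ALT or AST ≥5×ULN).
- Table 10-3 (Section 10.6.1), first row, covers the same pair of limits. It marks symptoms as not applicable, requires a hepatology consult, and classes the follow-up testing as essential: "Must have repeat liver chemistry values and additional testing completed ASAP", with a pointer to Section 10.6.1.3.

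**The concern.** The work-up table is where a potential Hy's Law case is sent, yet its PT/INR footnote uses stricter entry conditions than the rule that sends the child there. It brings back a symptom requirement that Table 10-3 sets aside, raises the transaminase limit and drops AST. A site following the protocol exactly would have no instruction to obtain a clotting test in many cases that require permanent discontinuation of lacosamide and reporting as an AE of special interest.

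At stake is the completeness of one safety measurement. In these children INR would be available or missing according to local practice rather than by protocol. No efficacy or safety estimate in the SAP depends on it.

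**Working it through.** No power, alpha or sample-size figure is involved, and the plan states no number to reproduce. The check compares the rules and then counts combinations.

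**The rules side by side**

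| Rule | Transaminase | Total bilirubin | Symptoms | Other |
|---|---|---|---|---|
| 10.3 potential Hy's Law | ALT or AST ≥3×ULN | ≥2×ULN | none | no ALP ≥2×ULN; no alternative explanation |
| 6.3.1 permanent stop | ALT or AST ≥3×ULN | ≥2×ULN | none | none |
| Table 10-3, row 1 | ALT or AST ≥3×ULN | ≥2×ULN | not applicable | hepatology consult |
| Table 10-4 footnote a (PT/INR) | ALT >8×ULN | elevated, no limit given | required | restricted by *only* |

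The ALT trigger is 8/3 = 2.67 times the potential Hy's Law limit and 8/5 = 1.6 times the 5×ULN stopping limit.

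**Combinations within potential Hy's Law.** Bilirubin is ≥2×ULN by definition, so the footnote's bilirubin condition is always met. Two yes/no conditions remain, giving 2 × 2 = 4 combinations:

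| ALT >8×ULN | Symptoms | PT/INR required, conditions joint | PT/INR required, any one condition |
|---|---|---|---|
| yes | yes | yes | yes |
| yes | no | no | yes |
| no | yes | no | yes |
| no | no | no | yes |

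On the joint reading INR is required in 1 of 4 and not in 3. A child whose elevation is in AST only falls in the two lower rows and has no required INR even with symptoms.

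**Finer grid.** An illustrative grid was also enumerated, with values chosen for the check rather than taken from the documents: ALT 1, 3, 5, 8, 8.1, 12; AST 1, 3, 5, 12; bilirubin 1, 1.5, 2, 3; ALP 1, 2 (all ×ULN); symptoms no or yes.

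- Potential Hy's Law biochemistry: of 6 × 4 = 24 ALT–AST pairs, all but (1, 1) qualify, so 23; times 2 bilirubin values, 1 ALP value and 2 symptom states = 92.
- PT/INR required, joint reading: 2 ALT values above 8 × 4 AST × 2 bilirubin × 1 ALP × 1 symptom state = 16.
- Not required: 92 − 16 = 76.
- Any-one reading: 92 of 92, because bilirubin alone suffices.

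One case in the gap is ALT 5×ULN, bilirubin 3×ULN, normal ALP, no symptoms. Another is AST 12×ULN with ALT ≤8×ULN and bilirubin 3×ULN, with or without symptoms.

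**Does other text supply INR?**

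- Section 10.6.1.3 allows extra tests, but on a different condition: "If the medical history of the subject indicates a requirement for other assessments not included below".
- Section 10.6.1.1 provides for a full hepatology assessment if judged necessary, and refers back to 10.6.1.3, where the same footnote applies.
- Section 10.6.1 says further investigation may be adapted once the cause is confirmed. That is permissive and names no test.
- Table 10-5 collects consult results if a consult was done, without specifying tests.
- Table 10-2, the routine panel, has no coagulation test.
- Section 10.6.1.4 and Table 10-3 require follow-up of liver chemistry only.

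None of these makes INR mandatory for a potential Hy's Law case.

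**The case against.** The strongest reply is that little turns on INR here. Once ALT or AST is ≥3×ULN with bilirubin ≥2×ULN, lacosamide is permanently stopped, a hepatology consult is required, and liver chemistry is repeated promptly and then at least twice weekly. Bilirubin and albumin are in the panel. A hepatologist may order an INR anyway, and Table 10-5 would collect the consult result. No passage gives INR a decision role, so the case for making it mandatory rests on general clinical judgement about its value. All of this stands. It limits the consequence, but it does not reconcile the footnote with the definition.

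Other points carry some weight:

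- **Standard wording and approvals.** The Amendment 2 rationale describes the PDILI text as standard across the sponsor's protocols, and Section 13.5 requires approvals for significant changes. This adds administrative cost.
- **Blood volume.** Subjects can be as young as 1 month (Section 6.1) and Table 10-4 is already a long panel. This is a real constraint for infants, and the site should plan for it.
- **Rarity.** Exclusion criterion 6 keeps out children with ALT, AST or ALP >2×ULN and most with raised bilirubin. Cases should be few, which also keeps the cost of the fix low.
- **Scope of Table 10-4.** Section 10.6.1.3 applies it when the drug may plausibly be the cause. Table 10-3 nevertheless calls the testing essential for this biochemistry, which largely answers the point.
- **An any-one reading of the footnote.** It would remove the gap, but the words *only* and *and* point the other way. Section 6.3.1 marks alternatives explicitly when it means them.

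**Conclusion.** The point holds. As written, the footnote leaves PT/INR unrequired in 3 of the 4 combinations of ALT level and symptoms possible within potential Hy's Law, including every case where the elevation is in AST only. The same mismatch applies to the ≥3×ULN with ≥2×ULN stopping rule in Section 6.3.1.

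This rests on reading the three conditions jointly, which is the plain sense, and on the claim being limited to INR that the protocol requires. The counts describe combinations; the documents give no distribution of ALT, AST, bilirubin or symptoms, so no patient frequency can be stated. If the sponsor meant the conditions as alternatives, the gap disappears in intent but the wording still needs correcting.

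This is a worthwhile, inexpensive safety improvement. It does not affect the trial's validity or its analyses.

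**What to change.** Reword footnote a so that PT/INR is measured at least in every subject with ALT or AST ≥3×ULN and total bilirubin ≥2×ULN, regardless of symptoms. These are the limits already used in Sections 6.3.1 and 10.3. The sponsor's physicians can keep ALT >8×ULN or symptoms as additional triggers, joined by *or*. All 4 combinations (92 of 92 on the grid) would then be covered.

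The cost is a change to one footnote, with whatever approvals Section 13.5 calls for, and at most one extra tube at a draw Table 10-3 already requires. For the youngest infants, the site should check total sample volume for the panel. No SAP change is needed.
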